1.2.1.1. Non Clinical Pharmacology

For further information refer to ENTO Investigator's Brochure (IB).

1.2.1.2. Toxicology

In vitro and in vivo nonclinical studies were conducted to examine the potential toxicity of ENTO. In vivo studies were conducted in rats and dogs. Oral administration is proposed for the initial clinical trials; therefore, multiple-dose studies with ENTO were conducted via the oral route (gavage).

Based on the totality of the data from the standard battery of in vitro and in vivo genotoxicity studies, ENTO is considered non-genotoxic.

Further details can be found in the ENTO IB.

1.2.2. Clinical Trials of Entospletinib (ENTO)

To date, 16 clinical studies have been initiated with ENTO including a total of 566 subjects (including 328 healthy subjects, 7 subjects with RA, 76 subjects with CLL, 155 subjects with NHL; 26 subjects receiving placebo in Phase 1 and Phase 2 clinical studies. Of the 540 subjects receiving ENTO in these studies, ENTO has generally been well tolerated.

Positive results have been reported from a Phase 2 clinical trial with the putative SYK inhibitor fostamatinib showing objective anti-tumor responses in chronic lymphocytic leukemia (CLL) and Non-Hodgkin's lymphoma (NHL) subjects {[Friedberg et al 2010](#)}. These responses occurred despite off target toxicities that limited drug exposure. ENTO is a highly selective inhibitor of SYK and hence has the potential for an improved efficacy and tolerability profile in subjects with hematologic malignancies.

ENTO is being evaluated in an ongoing Phase 2 clinical trial in subjects with relapsed or refractory CLL/NHL. A Phase 1b/2 clinical trial is being conducted for subjects with ENTO monotherapy and in combination with chemotherapy in subjects with acute myeloid leukemia (AML) and acute lymphocytic leukemia (ALL).

ENTO has been studied in single and multiple ascending dose studies in 304 healthy subjects, 7 subjects with rheumatoid arthritis who were on stable doses of methotrexate, 80 subjects with CLL and 95 subjects with NHL. Of these subjects, 460 received ENTO and 26 received placebo. In Pharmacokinetic (PK) studies at steady state in healthy subjects, ENTO was well tolerated when given in a fasted state for 7 days at doses of 25, 75, 200, 600, 900, and 1200 mg twice daily (GS-US-245-0101) and when given in a fed state for 6 days at doses of 100 and 900 mg twice daily (GS-US-245-0106), for 4 days at doses of 200 and 600 mg twice daily (GS-US-339-0101), and at 1200 mg twice daily for 5 days (GS-US-339-0109). Exposure, as measured by AUC and maximum concentration C_{max} , did not increase appreciably at doses above 600 mg under fasted condition.

To provide a margin for inter-patient variability, a dose of 900 mg twice daily was chosen for the study of subjects with rheumatoid arthritis receiving stable doses of methotrexate in Study GS-US-245-0101. A dose of 900 mg ENTO twice daily was given in a fasted state for 26 days in 7 subjects. The median AUC_{τ} in these subjects was similar to that of the healthy subjects. In general, this dose was well tolerated. One subject developed reversible, Grade 2 alkaline phosphatase and transaminase elevations starting 7 days after her last dose of ENTO, concurrent with new onset of a bronchopneumonia. One other subject reported not feeling well and experienced hot flashes, fever, shivers, rash, headache, dizziness, and fainting 1 day after her last dose of ENTO with reversible Grade 1 alkaline phosphatase and Grade 3 transaminase elevations which peaked 1 week later. While these events are potentially confounded by concurrent illnesses, hepatic enzymes will be closely monitored during this study.

Consistent with the known inhibition of UGT1A1 by ENTO, 8 of the 178 healthy subjects developed asymptomatic indirect bilirubin elevations (6 Grade 1, 1 Grade 2 and 1 Grade 3) that resolved following discontinuation of the drug. Three of the 7 subjects with rheumatoid arthritis who received ENTO for 26 days developed asymptomatic indirect bilirubin elevations (2 Grade 1, 1 Grade 3) which improved despite continued dosing.

Common AEs from an on-going Phase 2 study evaluating chronic administration of ENTO monotherapy in 186 subjects with hematologic malignancies are fatigue (53.2%), nausea (45.2%), diarrhea (38.7%), decreased appetite (24.7%), constipation (23.7%), cough (21.0%), and headache (21.0%) as of 21 November 2014. One out of a total of 201 subjects (0.5%) experienced pneumonitis in this monotherapy study as of 11 March 2015.

1.2.3. Interaction with Proton Pump Inhibitors

In Study GS-US-245-1222, omeprazole co-administration reduced ENTO AUC_{τ} by 59% following ENTO BIS-MSA 400 mg BID (solid dispersion formulation). Available solubility and clinical PK data strongly imply that the observed interaction between ENTO and PPIs is due to elevated gastric pH, leading to reduced ENTO absorption. ENTO solubility is known to be highly pH-dependent, with aqueous solubility of 10 mg/mL at pH 2 but <0.15 mg/mL at pH \geq 3.0, suggesting that PPIs are likely to reduce ENTO absorption due to increased gastric pH. In Study GS-US-245-1222, the ENTO terminal elimination half-life was similar when ENTO was administered alone (median [Q1, Q3] 14.89 [11.86, 21.36] hours) or with omeprazole (13.65 [10.49, 17.04] hours), demonstrating that the reduced ENTO exposure observed with omeprazole is likely a result of reduced absorption, rather than a result of altered elimination. Furthermore, omeprazole is a known inhibitor of CYP2C19 {[Angiolillo et al 2011](#)} however in vitro studies did not identify a role of CYP2C19 in ENTO metabolism. In addition, CYP inhibition by omeprazole would be expected to result in increased drug exposure of susceptible substrates, whereas significantly decreased ENTO exposure was observed with omeprazole co-administration in healthy volunteer studies.

Please refer to Section 1.4 of the protocol for further discussion of the dosing implications of PPI co-administration with ENTO in this study.

1.3. Rationale for This Study

Given the emerging role of B cells in cGVHD (abnormal response to BAFF, errors in B cell reconstitution/differentiation, BCR signaling via SYK or BTK, failed induction of B cell tolerance), ENTO, in a dose responsive manner, induces ex vivo apoptosis of a population of B cells present only in patients with active cGVHD, and the proof-of-concept studies with rituximab demonstrating that B cell targeted therapy shows benefit in cGVHD (see Section 1.1.1.1), Gilead is pursuing an investigation into whether ENTO is an effective treatment for cGVHD. Study GS-US-406-1840 is designed to evaluate the efficacy and tolerability of ENTO in addition to systemic corticosteroids in subjects at the time of initial diagnosis of cGVHD requiring treatment. Safety reviews will be performed in real time and will include evaluations of clinical laboratory abnormalities, relapse of primary malignancy, physical examinations, vital signs and AE reporting.

1.4. Rationale for Dose Selection

Since the target coverage necessary to achieve efficacy in subjects cannot be established in ex vivo experiments or animal models, the objective for dose selection is to achieve >50% target inhibition (% inhibition in stimulated CD63+ basophils) at trough. At 200 mg twice daily of ENTO BIS-MSA, the degree of inhibition of CD63+ cells is ~50% at steady state C_{trough} . However, the majority of cGVHD subjects are administered proton pump inhibitors (PPIs), which would be expected to decrease target inhibition below 50% at this dose. At an ENTO BIS-MSA dose of 400 mg twice daily in the presence of a PPI, target inhibition at C_{trough} is ~50%. Thus, the selected dose in cGVHD is 400 mg twice daily of ENTO in patients currently taking a PPI, and 200 mg twice daily of ENTO in patients not currently taking a PPI.

Furthermore, ENTO has a safety profile that is acceptable for subjects receiving treatment for malignancy (including cGVHD subjects). In studies with ENTO, the rate of Grade 3 or 4 AST/ALT elevations is between 10-14%, and these events are reversible with interruption of dosing. Reversible episodes of elevated indirect bilirubin (\geq Grade 1) occur in ~11% of subjects.

1.5. Risk/Benefit Assessment for the Study

Chronic GVHD remains a highly morbid disease with a high mortality rate, and given the cumulative safety data in healthy volunteers and patients with hematologic malignancies, the safety profile of ENTO is expected to be similar in cGVHD patients. ENTO is immunomodulatory, and even though ENTO has not been associated with an increased rate of infections in clinical studies in hematologic malignancy, serious infections are events of interest in this population as patients with cGVHD have a high rate of infections. Any immunomodulatory agent has a theoretical risk of decreasing the graft versus tumor effect, and malignancy relapse is also an event of interest in this study. However, as SYK inhibition affects primarily B cell function and not T-cell function, loss of the graft versus tumor effect is not expected as a result of treatment with ENTO. ENTO is associated with transaminase elevations and bilirubin increases, but these episodes have been reversible. The evaluation of safety of ENTO administration in the cGVHD population is facilitated in this study with the inclusion of a placebo control group.

Refer to the IB for full details of prior and ongoing pre-clinical and clinical studies including summary safety and efficacy data.

1.6. Compliance

This study will be conducted in compliance with this protocol, Good Clinical Practice (GCP), and all applicable regulatory requirements.

2. OBJECTIVES

The primary objective is:

To evaluate the effect of ENTO on the best overall response rate (BORR) as assessed by the cGVHD Activity Assessment (NCAA) by 24 weeks in the setting of add-on to systemic corticosteroids as part of first-line therapy for cGVHD

The key secondary objectives are:

- To evaluate the effect of ENTO on the skin domain of the Lee Symptom Scale (LSS) (Appendix 6) at 24 weeks
- To evaluate the effect of ENTO on the mouth domain of the LSS at 24 weeks
- To evaluate the effect of ENTO on the eyes domain of the LSS at 24 weeks
- To evaluate the effect of ENTO on the total score of the LSS at 24 weeks

Additional secondary objectives include:

- To evaluate the effect of ENTO on duration of response (DOR)
- To evaluate the effect of ENTO on dose reduction of corticosteroids
- To evaluate the effect of ENTO on initiation of second-line therapy for cGVHD
- To evaluate the effect of ENTO on progression of cGVHD
- To evaluate the safety and tolerability of ENTO

Exploratory objectives include:

- P [REDACTED]
- P [REDACTED]
- D [REDACTED]
- [REDACTED]
- [REDACTED]

3. STUDY DESIGN

3.1. Endpoints

The primary endpoint of this study is:

- The primary endpoint is BORR as assessed by the NCAA by 24 weeks in the setting of add-on to systemic corticosteroids as part of first-line therapy for cGVHD

[figure not shown]
The key secondary endpoints are:

- Change from Baseline in the skin domain of the LSS at 24 weeks
- Change from Baseline in the mouth domain of the LSS at 24 weeks
- Change from Baseline in the eyes domain of the LSS at 24 weeks
- Change from Baseline in the total score of the LSS at 24 weeks

Other secondary endpoints include:

- DOR
- Proportion of subjects who achieve at least 50% reduction in systemic corticosteroid dose relative to baseline
- Proportion of subjects who initiate second-line therapy for cGVHD
- Failure-free survival (FFS)
- Safety and tolerability of ENTO

Exploratory endpoints of this study include:

3.2. Study Design

This protocol describes a randomized, double-blind, placebo-controlled multicenter study to evaluate the efficacy and safety of ENTO (Treatment Arm 1) vs. placebo (Treatment Arm 2) in combination with systemic corticosteroids for subjects with cGVHD.

A total of 100 eligible subjects will be randomized in a 1:1 manner to ENTO (Treatment Arm 1) or placebo-to-match (PTM) (Treatment Arm 2), and treated for 48 weeks during the blinded phase. Randomization will be stratified by the following 2 factors at the Baseline/Day 1 Visit:

Stratification Factor	Stratification Levels
Calcineurin inhibitor or MMF use	Yes vs. No
Disease severity as determined by the 2014 NIH Consensus cGVHD criteria	Moderate cGVHD: 
 • ≥ 1 organ with score = 2, or • ≥ 3 organs with score = 1, or • lung score = 1 Severe cGVHD: 
 • any organ score = 3 or • lung score ≥ 2

The final analysis for BORR is planned when all subjects have been on study for 24 weeks. All subjects will be followed up to 48 weeks for DOR evaluation. At the Week 48 visit, subjects who are still on investigational treatment (ENTO or PTM) and are eligible to remain on study will have the option to receive open-label extension (OLE) with ENTO. This OLE offers patients who are deriving a benefit from ENTO or those with no alternative treatments the opportunity for further therapy for a serious and life threatening disease.

An external multidisciplinary data monitoring committee (DMC) will review the progress of the study, perform interim reviews of safety data at regular intervals approximately every 3 months, and perform an interim review of efficacy data for futility when approximately 50% of subjects have been on study for 24 weeks, as described in the DMC Charter. The first DMC meeting will be conducted after the 20th subject has been on study for 4 weeks. The DMC will provide recommendations to Gilead as to whether the nature, frequency, and severity of adverse effects associated with study treatment warrant the early termination of the study in the best interests of the participants, whether the study should continue as planned, or the study should continue with modifications.

3.3. Study Treatments

After 48 weeks of blinded treatment, subjects who are still on investigational treatment (ENTO or PTM) and are eligible to remain on study will have the option to receive open-label extension (OLE) with ENTO and attend visits per the schedule of assessments (Table 6-1) for an additional 96 weeks.

[figure not shown]
Subjects who provide written informed consent and meet all eligibility criteria will be randomized in a 1:1 fashion to either Treatment Arm 1 or Treatment Arm 2.

Subjects will return for study visits at Weeks: 2, 4, 8, 12, 16, 20, 24, 30, 36, 42 and 48. At the Week 48 visit subjects who are still on investigational treatment (ENTO or PTM) and are eligible to remain on study will have the option to participate in the OLE. If subjects elect not to enroll in the OLE phase of the trial, they will return for a 30-day follow-up visit.

Subjects that will continue in the OLE phase of the trial will return for the following study visits at Weeks: 50, 52, 56, 60, 64, 72 and visits every 12 weeks thereafter. **NOTE for subjects receiving tacrolimus, cyclosporine or MMF:** For subjects receiving these medicines at enrolment and are continuing on these medicines, the blood levels of tacrolimus, cyclosporine or the active metabolite of MMF (MPA) will be monitored at baseline/Day 1 (prior to starting ENTO or PTM), on Day 2 or Day 3 and Day 6 or Day 7 after initiating ENTO or PTM, and at the end of Week 2 and Week 50 study visit. Beyond these time points, concentration monitoring for tacrolimus, cyclosporine and MPA should follow the treating institution’s protocol and therapeutic range for monitoring these medicines. For subjects who initiate these medicines while already receiving ENTO or PTM, concentration monitoring for tacrolimus, cyclosporine and MPA should follow the treating institution’s protocol and therapeutic range for monitoring these medicines. When a concentration sample is taken at a local lab in accordance with the treating institution’s protocol for monitoring these medications, a sample may also be requested for central lab analysis.

PPD

Figure 3-1. Study Schema

- a Following the Baseline/ Day 1 visit subjects will return to the clinic for visits at Weeks 2, 4, 8, 12, 16, 20, 24, 30, 36, 42 and 48.
- b For subjects receiving tacrolimus, cyclosporine or MMF the blood levels of tacrolimus, cyclosporine or the active metabolite of MMF (MPA) will be monitored at baseline/Day 1 (prior to starting ENTO or PTM), on day 2 or day 3 and day 6 or day 7 after initiating ENTO or PTM, and at the end of Week 2 and Week 50 study visit. Beyond these time points, concentration monitoring for tacrolimus, cyclosporine and MPA should follow the treating institutions protocol and therapeutic range for monitoring these medicines
- c Subjects who complete the study through Week 48 and do not wish to continue to participate in the OLE phase of the trial will be required to return to the clinic 30 days after the completion of study drug for a 30-Day Follow-up visit
- d After Week 48, subjects who are still on investigational treatment (ENTO or PTM) and are eligible to remain on study will have the option to receive OLE for an additional 96 weeks. Subjects will attend visits at Weeks: 50, 52, 56, 60, 64, 72 and every 12 weeks thereafter.

- e The initial taper of prednisone from the starting dose of 1.0 mg/kg/day (or equivalent) may be attempted 14 days after co-administration with ENTO/Placebo if there is evidence of improvement in cGVHD

3.4. Discontinuation Criteria

Subject participation may be discontinued in the following instances:

- Intercurrent illness that would, in the judgment of the investigator, affect assessments of clinical status to a significant degree.
- Unacceptable toxicity, or toxicity that, in the judgment of the investigator, compromises the ability to continue study-specific procedures or is considered to not be in the subject's best interest
- Relapse of primary disease
- Severity of cGVHD requiring therapy that is not allowed as concomitant therapy on study (for example JAK inhibitor/BTK inhibitor /mTOR inhibitors/ any cell depletion agent/ phototherapy)
- Subject request to discontinue for any reason
- Subject noncompliance
- Pregnancy during the study; refer to [Appendix 8](#)
- Discontinuation of the study at the request of Gilead, a regulatory agency or an Institutional Review Board or Independent Ethics Committee (IRB/IEC)

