6.5. Post-treatment Assessments

6.5.1. Unscheduled Visit

A subject should attend an unscheduled visit if requested by the Sponsor or the investigator. The assessments performed are at the investigator's discretion.

For subjects that initiate second line therapy during the study, every attempt should be made to collect the NCAA and LSS at an unscheduled visit and to keep the subject in the study and study related follow-up procedures should be continued.

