6.5.2. Early Study Drug Discontinuation (ESDD)

If the subject discontinues study drug prior to the end of study, the subject will be asked to return to the clinic within 72 hours of stopping study drug for the Early Study Drug Discontinuation Visit. The subject will be asked to continue attending the schedule study visits through Week 48. Subjects who ESDD will not be eligible for the OLE phase of the study.

At the ESDD visit, any evaluations showing abnormal results indicating that there is a possible or probable causal relationship with the study drug, should be repeated weekly (or as often as deemed prudent by the investigator) until the abnormality is resolved, returns to baseline, or is otherwise explained.

Evaluation listed in [Table 6-1](#) will be completed at the ESDD visit.

The following will be conducted at the ESDD: review of adverse events (AEs) and changes in concomitant medications, vital signs (including weight), complete physical exam, primary malignancy assessment (if applicable), blood for hematology, chemistry, metabolic panel, selected biomarkers and urine for: pregnancy test (if applicable), and urinalysis. The NCAA and LSS will be assessed.

PFTs will be required at ESDD: spirometry with bronchodilator and diffusing capacity of the lungs for carbon monoxide (DLCO).

6.6. 30 Day Follow-Up Visit

Subjects who complete through Week 48 visit and who do not wish to participate in the OLE phase of the study will return to the clinic 30 days after the completion of study drug for the 30-Day follow-up visit. Subjects who complete the OLE will return to the clinic 30 days after the completion of study drug for the 30-Day follow-up visit

Subjects who permanently discontinue study drug and refuse to continue in the study will be asked to return to the clinic 30 days after the completion of the ESDD visit for the 30-Day follow-up visit.

For the purpose of scheduling a 30-Day follow-up visit, a ± 5 days window may be used. [Table 6-1](#) lists all procedures to be completed at the 30-Day Follow-up visit.

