6.11. Criteria for Discontinuation of Study Treatment

Study medication may be discontinued in the following instances:

- Intercurrent illness that would, in the judgment of the investigator, affect assessments of clinical status to a significant degree following resolution of intercurrent illness, the subject may resume study dosing at the discretion of the investigator.
- Unacceptable toxicity, or toxicity that, in the judgment of the investigator, compromises the ability to continue study-specific procedures or is considered to not be in the subject's best interest
- Relapse of primary disease
- Severity of cGVHD requiring therapy that is not allowed as concomitant therapy on study

- Subject request to discontinue for any reason
- Subject noncompliance
- Pregnancy during the study; refer to [Appendix 8](#)
- Discontinuation of the study at the request of Gilead, a regulatory agency or an institutional review board or independent ethics committee (IRB/IEC)

If the investigator considers discontinuing study medication for any reason other than those listed above, such as sustained complete remission of cGVHD for more than 3 months, then tapering to discontinue ENTO can be considered and should follow the schedule listed below:

Starting Dose	Action
400 mg twice daily	200 mg, twice daily, for 2 weeks
	200 mg once daily for 2 weeks
	200 mg, once daily, every other day for 2 weeks
	Stop Study Medication
200 mg twice daily	200 mg once daily for 2 weeks
	200 mg, once daily, every other day for 2 weeks
	Stop Study Medication

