6.4.2. Analysis Methods for Secondary Efficacy Endpoints

The key secondary endpoints will be analyzed using a two sample z-test at week 24.

Other secondary endpoints will be analyzed as follows:

DOR and FFS will be analyzed using the Kaplan-Meier (KM) method and stratified logrank test. Kaplan-Meier summary statistics (median, 95% CI for median, and 25th, 75th percentiles) and number and percentage of events will be presented by treatment group. A stratified Cox proportional hazards model will be used to estimate the hazard ratio and corresponding 95% CI. A KM survival plot will also be provided. Data for subjects who do not experience an event will be censored at the date of last visit. DOR will be analyzed only on subjects who responded.

Proportion of subjects with at least 50% reduction in systemic corticosteroid dose relative to baseline and proportion of subjects who initiated a second-line therapy for cGVHD will be analyzed similarly to the primary endpoint.

Line plot of change from baseline in each domain and total of LSS will be done.

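### Protocol 3.4 allows participation to end when cGVHD needs a disallowed therapy, whereas 6.11 stops study drug only and 6.5.1 and 6.5.2 keep the subject in follow-up, so outcome-related loss of the Week 24 LSS and of later second-line and FFS events is possible

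*Protocol*

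**What the plan says.** Two nearly identical lists govern different things.

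- **Protocol 3.4** opens with "Subject participation may be discontinued in the following instances". One item is "Severity of cGVHD requiring therapy that is not allowed as concomitant therapy on study", with JAK, BTK and mTOR inhibitors, cell-depleting agents and phototherapy as examples.
- **Protocol 6.11** opens with "Study medication may be discontinued in the following instances" and carries the same item without the examples.

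The follow-up sections point towards retention.

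- **Protocol 6.5.1**, for subjects who start second-line therapy: "every attempt should be made to collect the NCAA and LSS at an unscheduled visit and to keep the subject in the study".
- **Protocol 6.5.2**, for subjects who stop study drug early: "The subject will be asked to continue attending the schedule study visits through Week 48". At the early study drug discontinuation (ESDD) visit itself, "The NCAA and LSS will be assessed".
- **Protocol 5.1.1** takes the same line for unblinded subjects. They stop study treatment but are followed to study completion unless they withdraw consent to follow-up.

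On analysis, Protocol 8.1.3 makes receipt of second-line therapy a secondary endpoint and counts a documented change of systemic therapy as an FFS event. For FFS, SAP 6.4.2 adds: "Data for subjects who do not experience an event will be censored at the date of last visit".

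**The concern.** cGVHD that needs a disallowed therapy is treatment failure. A rule that lets a site end participation at that moment can remove subjects from observation because of how they are doing. Three sets of results depend on continued observation: the four key secondary LSS endpoints at Week 24, the proportion starting second-line therapy, and FFS. Loss tied to failure makes the Week 24 LSS values selectively missing and the FFS censoring informative. If failure differs between arms, so may the loss. Sites that read 3.4 literally and sites that read 6.5.1 and 6.5.2 literally would also collect different data on the same kind of subject.

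**Working it through.** The plan gives no figure for this loss, and no figure in the plan is disputed. The check is a comparison of passages.

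**1. Do the sections conflict?** For this item, 3.4 permits an end to participation, 6.11 covers study drug only, and 6.5.2 expects visits to continue after drug stops. Protocol 6.6 speaks of early discontinuers leaving only where the subject refuses to continue, which is not a site decision under 3.4. No section is given precedence, so the inconsistency is real.

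**2. How wide is it?** It is narrower than second-line therapy as a whole. Under 8.1.3, second-line therapy is any cGVHD therapy other than systemic corticosteroids or study drug, with inhaled and topical steroids excepted. The 3.4 item covers only therapy not allowed on study. Calcineurin inhibitors and MMF are not in Table 5-2, and Protocol 3.3 provides for subjects who start them during treatment. Those subjects do not meet the 3.4 item and remain under 6.5.1.

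**3. What is still captured when a subject leaves?**

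| Contact | NCAA and LSS | Concomitant medication | Limit |
|---|---|---|---|
| ESDD visit, within 72 hours of last dose | Yes | Yes | Misses therapy started afterwards |
| Start of second-line therapy (Table 6-1, footnotes g and h; 6.5.1) | Yes | Footnote r includes other immunosuppressive agents | Presupposes that the subject is still in the study |
| 30-day follow-up | Not scheduled | Yes | For early discontinuers, 6.6 asks this only of those who refuse to continue |

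The triggering therapy is therefore recorded if it starts by the last contact. It can be missed if it starts later, because the endpoint is receiving the therapy and not needing it.

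**4. Week 24 LSS.** SAP Table 1 sets the Week 24 window at Days 155 to 189. An ESDD assessment inside that window would count as Week 24. After an exit before Day 155, nothing replaces it. The SAP in force compares the arms with a two-sample z-test at Week 24 (6.4.2) and in general does not impute missing values (3.6.1). Its Appendix 6 deals with missing items and domains, not missing visits. Earlier LSS values then do not inform the comparison. Under the mixed model in Protocol 8.5.2 they would, which reduces the problem without removing it.

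**5. FFS.** If exit precedes a documented therapy change, death or relapse, the time is censored at the last visit for a reason linked to the coming event.

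**6. BORR.** This is the best response over all time points up to 24 weeks, so a response before exit already counts. Starting other systemic immunosuppression is itself progressive disease (Protocol Table 8-1, SAP Table 3), and the synopsis defines partial response as requiring no additional systemic therapy. Visits lost after such a start would rarely add a responder.

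**The case against.** The strongest answer is that 3.4 only says participation may end, while the operational sections press for retention. A careful site would follow 6.5.1 and 6.5.2, and the triggering therapy would often be on the ESDD record. This stands. A reader might infer that the endpoints go unmeasured in the subjects who fail. The documents do not support that, because it turns a permission into an outcome and overlooks the ESDD visit, Table 6-1 footnotes g, h and r, and the second-line agents that are allowed on study.

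A reader might also infer that the comparisons are pulled towards no difference by a calculable amount. That is not supported either. The plan gives no rate of disallowed therapy and no expected LSS change. Subjects kept in the study may improve on second-line therapy, so retaining them could itself narrow the difference between arms. The direction is open.

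It can further be said that only secondary endpoints are involved, that the z-test entered the SAP after early termination, and that SAP 3.5 now plans no formal comparisons. This limits the consequence for this trial. SAP 6.4.2 still specifies the LSS, second-line and FFS analyses, so their estimates would be affected by any such loss.

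What survives is that a permission to withdraw subjects for treatment failure stands beside sections asking for their follow-up, with no rule of precedence.

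**Conclusion.** The point holds as an unresolved inconsistency with a possible, outcome-related loss of data. A subject withdrawn under 3.4 before the Week 24 window opens would lack the Week 24 LSS. Second-line therapy starting after the last contact could be missed, as could any later FFS event, with FFS then censored. How often this would happen, and in which direction it would move the comparisons, cannot be derived from the documents, so no figure is offered. The conclusion rests on one assumption: that some sites would use the permission in 3.4. BORR is little affected. The matter should be corrected, but it does not threaten the primary analysis.

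**What to change.** Reconcile 3.4 with 6.11, 6.5.1 and 6.5.2. State in 3.4 that need for a disallowed cGVHD therapy is not in itself a reason to end participation. State that these subjects follow 6.5.1 and 6.5.2 unless consent is withdrawn: NCAA and LSS at the start of second-line therapy, its date and agent recorded, and scheduled visits through Week 48. The other items in 3.4 need not be rewritten for this purpose, and the rules for stopping treatment stay unchanged.

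The cost is a wording change in an amendment, plus some visits for subjects off drug that 6.5.2 already plans. For the report, SAP 4.1 already tabulates reasons for study-drug and study discontinuation separately. Exits for this reason before Week 24 can therefore be counted by arm, where the recorded reasons identify them, and shown beside the LSS, second-line and FFS results.
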